3.3.4.3. Quality of life and patient experience

Descriptive analyses will be carried out, also using bar graphs, of the items of the EQ-5D-5L and EORCT QLQ-LC29 questionnaires, comparing the pre- and post-operative values for each surgical approach. Starting from the results of the EQ-5D, the utility index associated with the health-related quality of life (HRQoL) will be calculated, and will be summarized through appropriate measures of position and variability for the three surgical approaches. Differences between surgical approach in terms of utility index will be estimated using a model for longitudinal data weighted by the inverse of the probability of surgical approach, similarly to what is described in the previous paragraph. As regards the PREMs questionnaires, descriptive analyses of the individual items will be carried out globally and by type of treatment.

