3.3.2. Prospective study design for the evaluation of quality of life and efficacy

All subjects who will undergo lung surgery (Table 1) during 2022 at the participating centers and will give their consent to participate in the study by signing the informed consent form at the prehospitalization or at hospitalization before surgery will be eligible to be enrolled. To evaluate the quality of life PROMs related, we will use the generic questionnaire EuroQol-5 Dimension (EQ-5D-5L) and the specific European Organization for Research and Treatment of Cancer Quality of Life Questionnaire-Lung Cancer (EORCT QLQ-LC29), which are available and validated in Italian [33,34]. The pre-intervention questionnaire will be completed on paper during hospitalization before the intervention or at pre-admission and the data will be entered into the web application of the ATS of Milan by dedicated staff. The subsequent questionnaires at day 7 and 30 can be self-completed by patients or electronically, using the dedicated web application of the ATS of Milan or in paper form, by filling in the documents issued on discharge for this purpose. At the first follow-up visit after 30 days, the patient will deliver the completed forms to the Thoracic Surgery department in charge of him. The Thoracic Surgery Department will forward all the documents, including pre-intervention documents, in a single mailing at the end of the study, to the Epidemiology Unit of ATS of Milan. The latter will enter the data and prepare it for subsequent analyses. The choice of how to complete the questionnaire will be left to the participating center. In both cases, when completing the first questionnaire, the study staff will enter the patient's fiscal code (patient identifier) in the application and a unique random ID will be generated which will be issued to the patient on paper so that he can enter it in the two subsequent self-compiled questionnaires. The information necessary for the evaluation of efficacy will be collected with the same modalities of the retrospective study. In addition to the evaluation of the quality of life, a questionnaire for the collection of patient experience (PREMs) will also be administered 30 days after the intervention or at the first follow-up visit [35,36]. The PREMs questionnaire will also be self-completed by patients either electronically, using the dedicated web application of the ATS of Milan, or in paper form, by filling in the document issued during hospitalization, the transmission of which to the Epidemiology Unit will take place with the methods indicated above.

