As regards the analysis of quality of life, the prospective study will take into consideration patients undergoing three types of surgery: robot-assisted, VATS, and open surgery. Specifically, the number of groups enrolled is assumed starting from the average of interventions carried out in the period 2016-2021. Therefore, for the prospective study, we estimated 48 subjects operated with robotic surgery, 94 with VATS, and 258 with open surgery. Literature relating to the comparison of the quality of life in patients operated with VATS and open surgery [38] illustrates the analysis of the EQ-5D questionnaire at different post-intervention time points. The data of our interest relate to the mean and standard deviation of the Visual Analogue Score of the EQ-5D questionnaire administered 4 weeks after the intervention; respectively: VATS 78.1, Open 73.5. The one-way analysis of variance methodology was used to study the power. For robotic surgery, since the necessary data in the literature are not available, we assumed an average of the Visual Analogue Score EQ-5D ranging from 80 to 83, which allowed the calculation of the estimated power illustrated in the table below. A standard deviation of 17.2 was assumed for all three groups based on literature data [38]. For the analysis of statistical power, we used the PROC POWER procedure, statement ONEWAYANOVA of the SAS software (v. 9.4, SAS Institute Inc., Cary, NC, USA).

Mean Visual Analogue Score EQ-5D	Power
80	0.669
81	0.790
82	0.880
83	0.939

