3.3.4.2. Efficacy study

Since this is an observational study, all analyses must take confounding into account. For each outcome, a Direct Acyclic Graph (DAG) will be prepared, discussed by surgeons and epidemiologists, i.e. a graph that allows hypothesizing the causal relationship between intervention and outcome taking into account potential confounding factors, measurable or not. On the basis of this graph, which underlies a causal model, the variables to be included in the multinomial regression model will be selected for estimating the probability of being treated with each surgical modality as a function of potential confounders (known as propensity score). Among the variables that will be considered to define the DAGs are age, gender, performance status, treatment center and tumor characteristics. The inverse of this estimated probability will be used as weight in the regression models (inverse probability weighted, IPW) which will have the outcome as the dependent variable and the treatment modality as the independent variable: robotics, VATS and thoracotomy (reference). Differences in the duration of surgery and hospitalization will be analysed using an IPW generalized linear regression model. The 30-day odds ratio (OR) of death for VATS and robotic surgery versus thoracotomy will be estimated by means of an IPW logistic regression model. Relative survival will be evaluated using a Cox IPW model and expressed both in terms of hazard ratio (HR) and as one and 5 year survival. For inpatient reoperation, the need for conversion to thoracotomy for VATS vs. robotic surgery and major complications by type of surgery, which are expected to be rare events, a we will consider a IPW zero-inflated (Poisson or negative binomial) approach. All estimates will be presented together with 95% confidence intervals obtained from a robust standard error [39]. The same analyses, if allowed by the study number, will be repeated in the three surgical subgroups (atypical and segmental resection, lobectomy, pneumonectomy), in subjects aged less than or equal to 65 years vs. superior, in patients with performance status of 0 vs. 1 vs. 2. Sensitivity analyses will be carried out using alternative models for the probability of estimating the type of intervention.

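### The role of the pre-operative EQ-5D in the utility comparison is not specified; it should enter both the model and the weights

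*Combined protocol and SAP*

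**What the plan says.** Section 3.3.2 collects the EQ-5D-5L and the QLQ-LC29 from prospective patients before surgery and at days 7 and 30. On the first of these: "The pre-intervention questionnaire will be completed on paper during hospitalization before the intervention or at pre-admission".

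Section 3.3.4.3 gives the pre-operative answers one explicit use, a descriptive before-and-after comparison within each approach. For inference, the difference in the utility index "will be estimated using a model for longitudinal data weighted by the inverse of the probability of surgical approach", with a reference back to section 3.3.4.2. No regressors, time terms or handling of the baseline value are given.

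Section 3.3.4.2 describes weighted regressions "which will have the outcome as the dependent variable and the treatment modality as the independent variable". The weights come from a multinomial propensity model whose variables are chosen from a causal graph drawn for each outcome. The candidates named are "age, gender, performance status, treatment center and tumor characteristics". They are given as examples, so the list is open, but baseline quality of life is not in it.

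Section 3.4.3 takes the QALY utilities from the EQ-5D answers and does not say whether raw or adjusted values are used. Section 3.4.2 sets a five-year horizon.

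**The concern.** The pre-operative value of the outcome is an obvious adjustment variable in a non-randomised comparison, and the plan pays to collect it. If patients chosen for robotic surgery start with better utility, and neither the weights nor the model account for this, part of that head start is read as an effect of the approach. Precision that the baseline would have supplied is also lost, in a comparison with about 48 robotic patients. If instead the baseline is fed in as one of three repeated responses with approach as the only term, the post-operative effect is diluted. Utilities feed the cost per QALY, so the choice can reach the main economic result.

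**Working it through.** **1. Reproduce the plan's power (section 3.3.4.1).** Inputs: "we estimated 48 subjects operated with robotic surgery, 94 with VATS, and 258 with open surgery"; comparator VAS means "respectively: VATS 78.1, Open 73.5"; for robotic surgery "we assumed an average of the Visual Analogue Score EQ-5D ranging from 80 to 83"; and "A standard deviation of 17.2 was assumed for all three groups based on literature data". Alpha is not stated for this calculation, so two-sided 5% is assumed.

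For a robotic mean m against open surgery, λ = (m − 73.5)² / [17.2² × (1/48 + 1/258)], with power from the non-central F on 1 and 397 df. At m = 80, λ = 42.25 / (295.84 × 0.02471) = 5.78 and power is 0.669. Means 81, 82 and 83 give 0.790, 0.880 and 0.939. All four stated values are matched. The overall three-group test would give 0.762, 0.834, 0.893 and 0.938. The table is therefore the robotic-open contrast on the raw four-week VAS, with no baseline term.

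**2. Add the baseline as a covariate.** The residual SD becomes 17.2 × √(1 − r²), with one df lost. The documents give no correlation r between baseline and follow-up, so a range is assumed. The residual SD is 16.4, 14.9 or 12.3 for r = 0.3, 0.5 or 0.7.

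| Robotic mean | Stated | r = 0.3 | r = 0.5 | r = 0.7 |
|---|---|---|---|---|
| 80 | 0.669 | 0.710 | 0.791 | 0.919 |
| 81 | 0.790 | 0.827 | 0.892 | 0.972 |
| 82 | 0.880 | 0.908 | 0.952 | 0.992 |
| 83 | 0.939 | 0.957 | 0.982 | 0.998 |

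These figures precede any loss from weighting. They are for the VAS, because the documents give no SD for the utility index. Robotic versus VATS stays weak: 0.095 to 0.360 unadjusted over means 80 to 83, and 0.111 to 0.456 at r = 0.5.

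**3. Bias from selection.** With equal SDs, a baseline difference d carries r × d into an unadjusted follow-up difference. A simulation (robotic versus open, near the planned 48/258 split, 3,000 runs) assumed that the log-odds of robotic surgery rise by 0.3 per baseline SD.
- Baseline in neither weights nor model: bias of about 0.09, 0.15 and 0.21 SD for r = 0.3, 0.5 and 0.7.
- Baseline in the weights alone: bias of about 0. The standard error at r = 0.5 is 0.152 SD, against 0.149 SD with baseline in both weights and model.

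**4. Baseline as a response in an approach-only model.** With three equally weighted responses, the approach coefficient is the mean of the three differences. For a constant post-operative effect δ it is [d + 2(δ + r × d)]/3 = 2δ/3 + d(1 + 2r)/3. The effect shrinks by one third, and a third of d enters directly, on top of the carry-over.

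**5. QALY scale.** Take an illustrative d = 0.03, about one standard error of the robotic-open baseline difference at an assumed utility SD of 0.20: 0.20 × √(1/48 + 1/258) = 0.031.
- Over 30 days at full carry-over: 0.03 × 30/365.25 = 0.0025. At r = 0.5, the trapezoid over days 0, 7 and 30 gives [3.5 × (0.03 + 0.015) + 11.5 × 2 × 0.015]/365.25 = 0.0014.
- Held for five years, with exponential survival and an assumed 50% or 65% alive at five years, undiscounted life-years are 3.61 or 4.06. At r = 0.5, 0.015 × 3.61 = 0.054 and 0.015 × 4.06 = 0.061. For r = 0.3 the range is 0.032 to 0.037, and for r = 0.7 it is 0.076 to 0.085.
- Section 3.3.4.1 uses a death probability of 0.8 without a time frame. Read as five-year mortality, it gives 2.49 life-years and 0.015 × 2.49 = 0.037.

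**The case against.** A reader might infer that the plan makes approach the sole regressor and discards the baseline. The documents do not say so. Section 3.3.4.3 lists no regressors, the reference back to 3.3.4.2 may concern only the weighting, and a longitudinal model would normally have time terms and could hold the pre-operative value as a response. Section 3.3.4.2 requires confounding to be addressed, draws a graph per outcome and leaves the candidate list open, so pre-operative utility could enter the weights. Step 3 shows that this alone would remove most of the bias and recover most of the precision. Performance status, a named candidate, may capture some of the imbalance too.

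All of that stands, so the bias is conditional on an unstated choice. It does not remove the need to state it. Efficacy is analysed jointly over about 5,000 retrospective and 400 prospective patients, and only the latter have a pre-operative EQ-5D. A propensity model carried over from the joint analysis could not contain it.

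Two further inferences fail. Chance imbalance is sampling error that an unadjusted interval already covers; it counts towards precision, not bias. And a loss of 0.11 to 0.12 QALY for d = 0.03 needs full carry-over of the imbalance, held for five years. The plan states neither, and full carry-over is inconsistent with r = 0.5. Nor does section 3.4.3 say that the modelled differences feed the QALYs.

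**Conclusion.** The point holds as a gap with a clear and better choice available: the plan collects the pre-operative EQ-5D and does not commit it to the utility model or the weights. The precision gain is the firmest part. At r = 0.5, robotic-open VAS power goes from 0.669 to 0.791 (mean 80) and from 0.790 to 0.892 (mean 81), given two-sided 5% and no allowance for weighting. Its transfer to the utility index is by analogy. The bias arises only if baseline is left out of both weights and model, and its size rests on the assumed selection strength. The QALY consequence runs from negligible over the 30 observed days to about 0.05 to 0.06 over five years for d = 0.03 at r = 0.5 and 50-65% survival. Where it falls depends on the extrapolation, which the plan should also state.

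**What to change.** In section 3.3.4.3, specify a model for day-7 and day-30 utility with approach, time, approach-by-time and pre-operative utility as a covariate, under the same weights. A constrained longitudinal model with a common baseline is an alternative. It presumes that weighting has equalised the baseline means, which is a further reason for the next change.

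Add pre-operative utility to the propensity model for the prospective quality-of-life analysis. In section 3.4.3, say that between-approach QALY differences rest on the baseline-adjusted estimates.

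Using the same model for the VAS and the QLQ-LC29 is optional, because sections 3.3.2.1 and 3.3.4.3 plan those results as descriptive.

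The cost is a few sentences in the plan, settled before the outcome data are analysed. No new data are needed.

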3.4. COSTS AND ECONOMIC EVALUATION

This is a *de novo* economic evaluation. The target population is the adult population undergoing lung surgery (atypical resection, segmentectomy, lobectomy, pneumonectomy) for benign or malignant pathology in the ATS of Milan, the intervention is the robotic surgical approach or computer-assisted surgery. This approach will be compared with both open surgery and VATS. The cost-effectiveness evaluation will be conducted according to the CHEERS (Consolidated Health Economic Evaluation Reporting Standards) guidelines [40].

3.4.1. Economic evaluation outcomes

The results of the cost estimates for each surgical approach will be summarized in tables and presented graphically. The outcome of the cost-effectiveness (CEA) and cost-utility (CUA) analysis will be the incremental cost-effectiveness ratio (ICER); in terms of cost per year of life gained for the first case and in terms of cost per QALYs earned for the second. The ICER of robotic surgery and VATS versus open surgery and the ICER of robotic surgery versus VATS will be calculated. A cost-effectiveness plan will also be constructed for these comparisons. Since the ICER alone cannot answer the question of whether a technology is cost-effective per se, it will be compared with a value in euros that society is willing to pay for an additional QALY earned ("societal willingness-to -pay"). Since there are no Italian regulatory references for willingness-to-pay, the references of NICE (£20-30,000), those of the Italian Association of Health Economics (€25-40,000) and the ICER calculated for dialysis (€50,000) will be used. Lastly, if the technology is cost-effective in at least one subgroup, a budget impact analysis will be carried out.

3.4.2. Point of view, time horizon

The point of view of both the cost-effectiveness and cost-utility evaluation is twofold. Initially, the point of view of the hospital structures will be adopted, therefore the direct health costs will be estimated, i.e. those relating to surgery, diagnostics, length of stay, health personnel, and drugs. These costs will be compared with the rate reimbursed for the DRG. Subsequently, the analysis will be extended to the point of view of society, considering indirect healthcare costs and non-healthcare costs, direct and indirect and intangible costs, evaluating the VAS and the utility index of the EQ-5D. The time horizon of the evaluation will be limited to 5 years from the intervention and the purchase of the technology. The tangible investments will be discounted according to the net present value method (marginal cost 5%/year and payment period of 5 years).

3.4.3. Model, clinical and cost input parameters

A decision tree model will be applied to summarize the consequences of the different interventions with regards to their clinical outcomes and costs incurred.

The input parameters for efficacy will be derived from the retrospective and prospective observational study. If further information becomes necessary, once the decision tree has been built, it will be calculated if possible by the court of the efficacy study. Otherwise, it will be derived from the literature. For the calculation of the QALYs, the utility values will be obtained starting from the results of the EQ-5D questionnaires prospectively administered to the patients, as described in paragraph 3.3.2., using the score function of van Hout et al. [41] and the Italian values of reference by Scalone et al [42].

For the input parameters of the costs, the identification of the resources will take place through a panel of expert thoracic surgeons and epidemiologists participating in the study. The quantification of resource consumption will take place using the administrative databases of the ATS with regard to pre-operative examinations, length of stay, follow-up visits, drugs and other identified direct health costs, using the same court identified for the efficacy study. To estimate the indirect health costs (patient travel, domestic assistance) the distance between the residence and the intervention hospital will be calculated for each patient. We will also use the estimate of the accesses number to the healthcare facility by surgical modality in the 30 days preceding and in the 6 months following the operation, using the administrative databases. For direct and indirect non-healthcare costs, such as the patient's lost days of work and lost productivity or early retirement, the *human capital approach* will be used.

For the allocation of costs strictly related to the surgical intervention with the three access modalities (purchase and maintenance of the instrumentation, duration of the intervention, personnel, etc.) a literature review will be performed. They will be compared with the rate reimbursed by the SNR per DRG. The determination of the unit cost for all other direct health costs (exams, visits, drugs) will be equal to the rate reimbursed by the regional health system, using the rates of the Lombardy region for hospital assistance, outpatient services and the prices of drugs agreed between AIFA and producer and published in the Italian Official Gazette. All costs will be expressed in euros.

3.4.4. Sensitivity analysis

Since the costs are volume-dependent, the effect of a different number of cases on the costs and therefore on the cost-effectiveness with respect to the measured volumes will be evaluated. Furthermore, to evaluate the robustness of the model, deterministic sensitivity analyzes will be performed to evaluate the fluctuation of the results as the parameter values vary with respect to the

minimum and maximum of the confidence interval. Univariate analysis will be presented by tornadoplot.

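### The economic evaluation plans only deterministic, one-way sensitivity analysis, so the cost-effectiveness verdict will carry no measure of joint uncertainty

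*Combined protocol and SAP*

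**What the plan says.** Section 3.4.4 is the whole of the plan's uncertainty analysis for the economic evaluation. It has two parts. The first is a scenario on surgical volume, because costs depend on volume. The second is that "deterministic sensitivity analyzes will be performed to evaluate the fluctuation of the results as the parameter values vary" between the limits of their confidence intervals, and "Univariate analysis will be presented by tornadoplot".

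Section 3.4.1 sets the output: "The ICER of robotic surgery and VATS versus open surgery and the ICER of robotic surgery versus VATS will be calculated". Because an ICER does not settle the question alone, "it will be compared with a value in euros that society is willing to pay for an additional QALY earned"; the reference values are £20,000–30,000, €25,000–40,000 and €50,000. A plane is also planned: "A cost-effectiveness plan will also be constructed for these comparisons" (evidently the cost-effectiveness plane). A favourable result in even one subgroup leads to a budget impact analysis.

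The 95% confidence intervals promised in 3.3.4.2 belong to the clinical estimates. Section 3.4 (economic evaluation) provides none for the ICER.

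**The concern.** The cost-effectiveness comparison is the primary objective (2.1), and section 7 expects the study to settle whether the technology is cost-effective locally. That verdict combines three uncertain inputs:

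- **Survival**, from a weighted Cox model (3.3.4.2).
- **Utility.** According to 3.3.4.3, "Differences between surgical approach in terms of utility index will be estimated using a model for longitudinal data". The prospective cohort is expected to be small in the robotic arm: "we estimated 48 subjects operated with robotic surgery, 94 with VATS, and 258 with open surgery". Questionnaires stop at about day 30 (3.3.2), against a 5-year horizon (3.4.2).
- **Surgical cost**, taken from a literature review (3.4.3).

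Moving one input at a time to its limits shows which input matters most. It carries no joint distribution of cost and effect, so it cannot say how often the true result falls on the other side of a threshold. A verdict close to a coin toss could be reported as a clear pass.

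**Working it through.** **Step 1: text check.** Sections 3.3.4 and 3.4, and the rest of the document, contain no probabilistic sensitivity analysis, Monte Carlo simulation, bootstrap, parameter distribution, acceptability curve, net benefit or ICER interval. The plan states no ICER or probability of cost-effectiveness, so there is no figure of its own to reproduce. What follows is an illustration.

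**Step 2: precision of the hazard ratio, from the plan's inputs.** From 3.3.4.1: n = 5400, probability of death 0.8, robotic share 0.12. The plan's formula gives SE(ln HR) = 1/√(5400 × 0.12 × 0.88 × 0.8) = 0.0468. With one-sided alpha 0.05 (assumed, because the printed value is incomplete), power is Φ(ln 1.08/0.0468 − 1.645) = 0.50 and Φ(ln 1.15/0.0468 − 1.645) = 0.91. These match the plan's range, so the inputs are read correctly.

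For the planned contrasts, apply the 48/94/258 split of 400 to all 5400 (an assumption): 648 robotic, 1269 VATS, 3483 open. Deaths at 0.8 are 518.4, 1015.2 and 2786.4. With SE = √(1/d₁ + 1/d₂) and no loss from weighting:

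- robotic vs open: 0.0478
- robotic vs VATS: 0.0540
- VATS vs open: 0.0367

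**Step 3: base case, all values assumed.** HR 0.95 robotic vs open; exponential survival with 20% alive at 5 years, so λ = −ln(0.2)/5 = 0.3219; utility 0.8 in both groups; extra cost €2,000; effects undiscounted.

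LY(HR) = (1 − exp(−5λHR))/(λHR). LY(1) = 2.4853 and LY(0.95) = 2.5613. The gain is 0.0760 life-years, or × 0.8 = 0.0608 QALY. ICER = 2000/0.0608 ≈ €32,900. As a point estimate, this passes at €40,000.

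**Step 4: probability of being cost-effective, hazard-ratio uncertainty only.** At threshold k the QALY gain must be at least 2000/k. Dividing by 0.8 and solving LY(HR) − LY(1) gives the largest HR that still passes (HR*). The probability is Φ(ln(HR*/0.95)/0.0478).

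| Threshold | QALY needed | HR* | Probability |
|---|---|---|---|
| €25,000 | 0.08 | 0.9347 | 0.37 |
| €40,000 | 0.05 | 0.9587 | 0.58 |
| €50,000 | 0.04 | 0.9668 | 0.64 |

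The probability of fewer QALYs with robotic surgery is Φ(ln 0.95/0.0478) = Φ(−1.07) = 0.14.

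**Step 5: add utility sampling error.** Let the utility difference be centred on 0 and last 5 years, with SE = SD × √(1/48 + 1/258) = 0.157 × SD. By simulation (2 million draws), the probability at €40,000 is 0.56 for an assumed SD of 0.10 and 0.54 for 0.20. The probability of fewer QALYs rises to 0.19 and 0.27. Cost is held fixed throughout.

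**Step 6: sensitivity to the share of deaths.** Vital status is read at 31 December 2022 (Table 4). Under the same curve, with even accrual over 2016–2021 (follow-up 1 to 7 years), the mean proportion dead is 1 − (e^(−0.3219) − e^(−2.2532))/(6 × 0.3219) = 0.68. For 400 patients spread over 2022 it is 1 − (1 − e^(−0.3219))/0.3219 = 0.145. Overall: (5000 × 0.68 + 400 × 0.145)/5400 ≈ 0.64. The robotic-vs-open SE becomes 0.0478 × √(0.8/0.64) = 0.053, and the probability at €40,000 is 0.57. The picture does not change.

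**Step 7: quality-of-life precision from the plan's own figures.** Section 3.3.4.1 assumes EQ-5D VAS means of 80–83 (robotic) and 78.1 (VATS), SD 17.2. The SE of the robotic–VATS difference is 17.2 × √(1/48 + 1/94) = 3.05. The difference is 1.9 (95% CI −4.1 to 7.9) to 4.9 (−1.1 to 10.9), and the estimate would be negative with probability 0.27 to 0.05. This is the VAS, unweighted and with full response. The plan gives no sizing for the utility index that feeds the QALYs.

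**The case against.** **The plan never promises a probability.** It promises ICERs set against thresholds, and it delivers them. That is fair: there is no internal contradiction and no wrong number. The point is that a clearly better method is available from data already planned.

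**The plane, CHEERS and multi-way runs.** The plane places a point estimate in a quadrant, but no scatter or interval is specified for it. Section 3.4 says the evaluation will follow CHEERS, yet the only uncertainty method written down is deterministic. The wording does not exclude multi-way deterministic runs, but none is specified and none would yield a probability.

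**The illustration is invented.** The €2,000, the utilities and HR 0.95 are assumptions. The HRs used in the plan's power calculation are 1.08–1.15. The introduction reports robotic surgery as dearer in the literature but also lists offsetting savings. The figures therefore show what a joint analysis adds, and do not predict the result.

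**A stronger reading to resist.** A reader might infer that, with no rule for a negative ICER, the plan will misread a costlier and less effective result as favourable, or print tornado limits in the wrong order. The documents do not support this. Section 3.4.4 refers only to the results and does not say the tornado is drawn on the ICER. A sign problem there would also need robotic surgery to cost more and an input's limits to take the effect through zero. The planned plane already separates quadrants for a point estimate. Nor does the missing label cause the missing probability; only the absence of a joint analysis does.

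**Conclusion.** The point holds as a gap in the planned analysis. Section 3.4.4 is confined to a volume scenario and deterministic variation, and no other section supplies a joint uncertainty analysis or an ICER interval. The primary conclusion would therefore have no stated decision uncertainty.

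Its size cannot be computed from the documents, which give no incremental cost, incremental QALY or variance for either. On the assumptions in steps 2 to 5, an ICER that passes at €40,000 has a probability of 0.54 to 0.58 of being cost-effective there. Other inputs would give other values. This is an improvement the sponsor should make, not the correction of an error. The handling of negative ICERs is a minor matter of presentation.

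**What to change.** **In 3.4.4**, add a probabilistic sensitivity analysis for robotic vs open, robotic vs VATS and VATS vs open:

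- Bootstrap the inputs derived from the cohort, re-estimating the propensity weights in each resample.
- State distributions for the utilities, including how long any difference is taken to last after day 30, and for the literature-based surgical costs.
- Show the draws on the cost-effectiveness plane already planned.
- For cost per QALY, report an acceptability curve over the 3.4.1 thresholds, with the pound values converted to euros at a stated rate.
- For cost per life-year, where 3.4.1 gives no threshold, report the plane and a curve over a stated range.

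The tornado plot can stay as it is.

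**In 3.4.1** (minor), report a result as dominant or dominated instead of printing a negative ICER.

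**Cost:** wording in two sections, extra analysis work, and the need to choose and justify the distributions, preferably before results are seen. No new patient data are needed.
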